## **8.4 Vital Signs, Pulse-Oximetry, Height, Weight, and EKG Assessments**

Using descriptive statistics, continuous data describing vital signs, oxygen saturation (through pulse oximetry), and 12-lead EKG results will be summarized by time-point within a single table. Vital signs will include heart rate, respiratory rate, systolic and diastolic blood pressure, and body temperature, whereas EKG measures will include heart rate and QT interval with Fridericia's correction. The details of all vital sign measurements, as well as patient body height and weight, will be disclosed in a single patient-level data listing. In addition to these data presentations, a separate table will be generated to summarize the numbers and percentages of patients who show shifts from baseline in overall interpretation of EKG results (normal, abnormal non-clinically significant, and abnormal clinically significant) by time-point, and a separate patient-level data listing will be dedicated to individual EKG results.

## **8.5 Physical Examinations**

Multiple physical examinations will be performed during the period of screening through the Day-6 visit. Findings deemed clinically significant during screening will be recorded as medical history, whereas clinically-significant findings from all later exams will be captured as TEAEs. To disclose the details of all exam findings, regardless of clinical significance, a patient-level data listing will be provided.

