**Table 4. Schedule of Events**

Evaluation	Initial Screen	Rescreen (if applicable  )	Day 1  Base Line -2 hr pre-infusion	1 hr post infusion ± 15min	6 hr post -1 or +2 hr	Day 2 24 hr post ± 3 hr	If hospitalized			Day 6 (+ 4 days)	Day 30 (+2 days) (by phone)
							Day 3	Day 4	Day 5		
Visit #	1	1A	2	3	4	5	6	7	8	9	10
Sign ICF	X										
Verbal reconfirmation of informed consent		X	X	X	X	X	X	X	X	X	X
History and complete physical exam 	X										
WHO assessment	X	X	X	X	X	X				X	
Abbreviated physical exam 		X	X	X	X	X				X	
Pregnancy test (serum or urine)-applicable females only	X	X									
Concomitant medications (Medications, OTC Remedies, Herbal Preparations,	X	X	X	X	X	X	X	X	X	X	

Evaluation	Initial Screen	Rescreen (if applicable  )	Day 1  Base Line -2 hr pre-infusion	1 hr post infusion ± 15min	6 hr post -1 or +2 hr	Day 2 24 hr post ± 3 hr	If hospitalized			Day 6 (+ 4 days)	Day 30 (+2 days) (by phone)
							Day 3	Day 4	Day 5		
Vitamins, Supplements and IV fluids)											
Record transfused blood products 	X	X	X	X	X	X	X	X	X	X	
Infusion			X								
Vital signs (pulse, BP, RR, temp)	X	X	X	Prior to infusion and then every 15 min ±5 min after the start of infusion until 2 hrs; continue every hour ±5 min until 4 hrs, then at 6 hrs, and 24 hrs post infusion.						X	
Pulse-Ox			X	Continuously monitor while monitoring for vital signs; record at same time points as for vital signs above.							
Monitor for AE			X	Prior to infusion and then every 15 min ±5 min after the start of infusion until 2 hrs; continue every hour ±5 min until 4 hrs, then at 6 hrs, and 24 hrs post infusion, ±10 mins for all other time points. Daily until discharged or Day 6.			X	X	X	X	X 
12-Lead EKG	X		X 		X						

Evaluation	Initial Screen	Rescreen (if applicable  )	Day 1  Base Line -2 hr pre-infusion	1 hr post infusion ± 15min	6 hr post -1 or +2 hr	Day 2 24 hr post ± 3 hr	If hospitalized			Day 6 (+ 4 days)	Day 30 (+2 days) (by phone)
							Day 3	Day 4	Day 5		
Hematology CBC (if blood products are transfused, then CBC pre and post transfusion)	X	X	X	X	X	X	Minimum is daily CBC			X	
ABO group, Rh type	X										
Coagulation Tests: PT/INR, aPTT, D-dimer, Fibrinogen, TAT, PF 1+2, TEG or ROTEM, TGA	Only PT/INR, aPTT, D-dimer, Fibrinogen	Only PT/INR, aPTT, D-dimer, Fibrinogen	X	X	X	X					

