### 3.3 Summary of Activities and Assessments

**Table 2 – Schedule of Activities and Assessments, Modified from CSP 2017-1 Table 4**

Evaluation	Initial Screen	Rescreen 	Day 1 (baseline) 	1-h post-infusion ±15 min	6-h post-infusion -1 or +2 h	Day 2 24-h post-infusion ±3 h	If hospitalized			Day 6 (+4 d)	Day 30 (+2 d) (via phone)
							Day 3	Day 4	Day 5		
Visit Number:	1	1A	2	3	4	5	6	7	8	9	10
Sign informed consent form	X										
Verbally reconfirm consent		X	X	X	X	X	X	X	X	X	X
Medical history and complete physical exam 	X										
WHO bleeding severity	X	X	X	X	X	X				X	
Abbreviated physical exam 		X	X	X	X	X				X	
Pregnancy test (female only)	X	X									
Concomitant medications 	X	X	X	X	X	X	X	X	X	X	
Record transfused blood products 	X	X	X	X	X	X	X	X	X	X	
Thrombosomes infusion			X								
Vital signs 	X	X	X	Prior to infusion, then every 15 ±5 min after start of infusion until 2 h. Continue every 1 h ±5 min until 4 h, then at 6 h and 24 h ±10 min post-infusion.						X	
Pulse oximetry			X	Monitor continuously during vital signs assessment; record at same time-points as vital signs.							
Monitor for AEs			X	Prior to infusion, then every 15 ±5 min after start of infusion until 2 h. Continue every 1 h ±5 min until 4 h, then at 6 h and 24 h ±10 min post-infusion. Continue daily monitoring until discharged or Day 6.				X	X	X	X 
12-lead EKG 	X		X 		X						
Hematology CBC 	X	X	X	X	X	X	Daily CBC, at minimum		X		
ABO group, Rh type	X										
Coagulation testing 	X	X	X	X	X	X					
Routine chemistry 			X		X	X					
Special chemistry 			X		X	X					
Draw archive sample 	X									X	

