## 6.2 Nominal Visits and Visit Windows

For each patient, infusion of Thrombosomes will occur on Day 1. Screening, baseline (pre-infusion), and post-infusion activities and assessments will correspond to specific nominal visits and time-points, as shown below in **Table 3**. Note that each nominal visit/time-point has an associated window, defined as the range in time (e.g., study days, hours, or minutes) during which the scheduled activities or assessments must be performed. Activities and assessments performed outside of these windows will be labeled “unscheduled”. Data collected from unscheduled activities/assessments will be incorporated into patient-level data listings but will not necessarily be included in population-level data summaries (i.e., tables and/or figures) presented by visit/time-point. As appropriate (e.g., depending on sample size), data from unscheduled visits/time-points will be either entirely excluded from data summaries or compiled between scheduled visits/time-points for intermixed scheduled/unscheduled data presentation.

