**Table 3 – List of Nominal Visits and Time-Points**

Nominal Visit/Time-Point	Scheduled Study Day	Day/Time Window
Screening 	Days -28 to Day -1	Any time during Days -28 to Day -1
Baseline	Day 1	Any time pre-infusion during Day 1 
Thrombosomes Infusion	Day 1	None; represents time-point 0 and provides reference for nominal visits and time-points
1-hour post-infusion	Day 1	±15 minutes
6-hour post-infusion	Day 1	-1 to +2 hours
24-hour post-infusion	Day 2	±3 hours
Day 3 	Day 3	Any time during Day 3
Day 4 	Day 4	Any time during Day 4
Day 5 	Day 5	Any time during Day 5
Day 6	Day 6	+4 days (any time during Days 6-10)
Day 30	Day 30	+2 days (any time during Days 30-32)

 If the patient is not actively bleeding at the time of screening but bleeding occurs within 4 days (+6 hours) of initial screening, the patient will not be rescreened (just WHO bleeding severity and CBC assessments will be repeated). If the patient is not actively bleeding at the time of screening but bleeding occurs >4 days and within 4 weeks of initial screening, the patient will be wholly rescreened and, following verification of eligibility, then enrolled and infused.

 Baseline assessments may occur any time preceding infusion on Day 1, except for the assessments of WHO bleeding severity, CBC, and coagulation. These assessments will be required to occur within the 2 hours preceding infusion.

 Relevant only if the patient is hospitalized.

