## 6.3 Data Derivations based on Timing

For a given date within the screening period, the sequence number identifying the study day will be computed as the relevant screening date minus the date of Day 1 (i.e., screening date – date of Day 1). For a given date on/following infusion with Thrombosomes, the sequence number identifying the study day will be computed as the relevant infusion (or post-infusion) date minus

the date of Day 1 plus 1 day (i.e., infusion or post-infusion date – date of Day 1 + 1) to allow for inclusion of Day 1 within the computed period.

The following will define prior medication use versus concomitant medication use:

- Prior medication – any medication last used by a patient within the 4 weeks immediately preceding the date of Thrombosomes infusion. Anti-coagulant medications represent an exception, with the applicable range in dates ending at 48 hours before infusion.
- Concomitant medication – any medication taken on or after the date of Thrombosomes infusion through the Day-6 visit. Anti-coagulant medications represent an exception, defined as concomitant if taken at any time during the 48 hours preceding infusion through the Day-6 visit.

Baseline values for all assessment variables will be based on data collected during the latest assessment procedure performed prior to infusion with Thrombosomes. Unless otherwise specified, the change-from-baseline (CFB) value corresponding to any quantitative post-infusion assessment variable will be calculated by subtracting the baseline assessment value from the relevant post-infusion assessment value. If either the baseline or post-infusion assessment value is missing, then the CFB value will also be set to missing.

Pre-treatment AEs and treatment-emergent AEs (TEAEs) will adhere to straightforward definitions, with pre-treatment events occurring prior to start of the Thrombosomes infusion on Day 1 and treatment-emergent events occurring at or following the start of infusion.

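### SAP 8.5 makes clinically significant findings from the Day 1 pre-infusion exam TEAEs, which contradicts the infusion-start definition in SAP 6.3

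*SAP*

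**What the plan says.** SAP 8.5 sorts physical exam findings by the visit at which they are seen. The first part of its rule is "Findings deemed clinically significant during screening will be recorded as medical history"; the second is that "clinically-significant findings from all later exams will be captured as TEAEs". It does not test onset against the time of infusion.

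SAP 6.3 sorts AEs by time, with "pre-treatment events occurring prior to start of the Thrombosomes infusion on Day 1 and treatment-emergent events occurring at or following the start of infusion". SAP 3.2 likewise describes AEs by timing relative to infusion start, and SAP 8.1 tabulates pre-treatment AEs and TEAEs as separate categories.

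The row "Abbreviated physical exam" in SAP Table 2 is marked at rescreening, Day 1 baseline, 1 hour, 6 hours, 24 hours and Day 6. Protocol Table 4 has the same schedule and heads the Day 1 column "Base Line -2 hr pre-infusion". SAP Table 3 gives the baseline window as "Any time pre-infusion during Day 1".

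SAP 2.2.1 lists first among the primary endpoints the frequency of TEAEs and serious TEAEs, and the number and percentage of patients who have them.

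**The concern.** The Day 1 baseline exam comes after screening and before infusion. Section 8.5 makes a clinically significant finding at that exam a TEAE; section 6.3 makes it a pre-treatment AE. The SAP does not say which section prevails, so two programmers who each follow the text could report different counts for the first primary endpoint.

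Such findings are plausible in this population. A patient who is not bleeding at screening but starts within 4 days (+6 hours) repeats only the WHO assessment and the CBC. For that patient, the Day 1 baseline exam is the first scheduled abbreviated exam after the bleed begins. It covers the head and neck, and the qualifying Grade 1 bleeds include epistaxis, oral petechiae and oropharyngeal bleeding. If the investigator judges the sign clinically significant, 8.5 as written could turn the bleed that made the patient eligible into a treatment-emergent event.

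**Working it through.** **Step 1. Is the baseline exam a later exam under 8.5?** SAP 6.2 treats the periods as distinct: "Screening, baseline (pre-infusion), and post-infusion activities and assessments will correspond to specific nominal visits". Table 3 ends screening at Day -1 and puts baseline on Day 1. SAP 3.1 does gloss the pre-infusion period as screening, but it lists Day 1 separately. So the baseline exam falls outside screening and inside 8.5's second rule.

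**Step 2. Do the two rules disagree?**

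| Exam | Under SAP 8.5 | Under SAP 6.3 |
|---|---|---|
| Initial screening | Medical history | Before infusion |
| Rescreening | Not stated; can be read as screening | Before infusion |
| Day 1 baseline | TEAE | Pre-treatment AE |
| 1 h, 6 h, 24 h, Day 6 | TEAE | TEAE if onset is at or after infusion start |

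The clear conflict is in the Day 1 baseline row. Five exams are scheduled from baseline on, and four of them follow infusion. There is a second, smaller gap in the last row: 8.5 does not ask whether a later finding is new, so a screening finding that is still present at 1 hour is, read literally, also captured as a TEAE.

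**Step 3. How much could it matter?** The plan states no figure for this point. The denominators are 8 per cohort and 3 × 8 = 24 overall (SAP 3.1).

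Shift per patient whose only TEAE is a pre-infusion finding:

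- Cohort: 1/8 = 12.5 percentage points.
- Overall: 1/24 = 4.2 percentage points.

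Let p be the share of patients with a clinically significant finding at the Day 1 pre-infusion exam. The documents do not give p; 5%, 10% and 20% are assumptions. The chance of at least one such patient among n is 1 − (1 − p)^n, and the expected number among 24 is 24p.

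| Assumed p | At least one of 8 | At least one of 24 | Expected among 24 |
|---|---|---|---|
| 5% | 1 − 0.95^8 = 34% | 71% | 1.2 |
| 10% | 1 − 0.90^8 = 57% | 92% | 2.4 |
| 20% | 1 − 0.80^8 = 83% | 99.5% | 4.8 |

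A patient who also has a true TEAE is already in the numerator. Let q be the share with a true TEAE (also assumed), independent of the baseline finding. The expected rise in the percentage of patients is then p(1 − q):

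| Assumed q | p = 5% | p = 10% | p = 20% |
|---|---|---|---|
| 30% | 3.5 points | 7 points | 14 points |
| 50% | 2.5 points | 5 points | 10 points |
| 80% | 1 point | 2 points | 4 points |

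The count of events, which is also part of the endpoint, rises by one for each such finding whatever q is.

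**Step 4. After alignment with 6.3.** Findings from the Day 1 pre-infusion exam add no TEAEs, and the four post-infusion exams remain as possible sources.

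**The case against.** The strongest reply is that 6.3 is the operative definition. It sits in the section on timing derivations, 3.2 and 8.1 are consistent with it, and SAP Table 2 starts AE monitoring before infusion, so pre-treatment AEs are an expected category. Section 8.5 is a short passage on where exam findings are recorded, and its only output is a listing. If the TEAE flag is programmed from onset time, nothing is inflated. This stands as a limit on the consequence. It does not remove the conflict, because nothing in the SAP gives 6.3 precedence over 8.5.

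A reader might infer three further things that the documents do not support.

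- **Rescreening findings also become TEAEs.** Table 3 has a single screening row, and its footnote on rescreening is attached to that row. Rescreening can therefore be read as part of screening, and 8.5 does not settle it.
- **The overstatement is large, for example 25 points in a cohort.** That needs 2 of 8 patients with a baseline finding and no other TEAE (2/8 = 25%). No document supplies such a rate. The sicker the patients are assumed to be, the fewer are likely to have no true TEAE.
- **Dose escalation would be distorted.** The DMC does receive TEAE summaries, but no TEAE-rate threshold governs suspension, stopping or escalation. Suspension and stopping turn on SAEs judged related to the product, and stopping also on event type and a time window. Nothing shows that a decision would change.

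**Conclusion.** The contradiction holds. For the Day 1 pre-infusion exam, SAP 8.5 as written assigns findings to a category that 6.3 denies them, and the category feeds the first primary endpoint. If 8.5 is followed, the error can only add to the TEAE count.

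A reader might go further and conclude that the primary endpoint is inflated. The documents do not support that as a certainty, since it happens only if 8.5 is applied over 6.3, 3.2 and 8.1. The size is also unknown. The firm figures are 12.5 points in a cohort of 8 and 4.2 points among 24 for each patient whose only TEAE is a pre-infusion finding. The probabilities and expected rises rest on assumed rates and, for the rises, on independence of baseline findings and true TEAEs.

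**What to change.** Reword SAP 8.5 so that:

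- clinically significant findings at screening are medical history, stating that screening includes rescreening;
- findings first noted at the Day 1 pre-infusion exam are pre-treatment AEs;
- findings with onset at or after infusion start are TEAEs, by reference to 6.3.

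An onset test in the last item also keeps persisting screening findings out of the TEAE count. If worsening of a pre-existing finding is meant to count as a TEAE, say so in 6.3, so that it applies to all AEs; 6.3 now uses timing alone, and adding worsening only to 8.5 would create a new mismatch.

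The onset rule depends on clock times on Day 1. SAP 6.4 imputes a missing start time to the beginning of the day, which would place a Day 1 event before infusion, so onset times should be recorded for Day 1 findings.

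The cost is a rewording of 8.5 and, if worsening is to count, a clause in 6.3. No new assessment or analysis is needed.

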## 8.6 Infused Thrombosomes

A tabular summary of statistics describing the Thrombosomes infusion doses received by patients will be provided. Specifically, the statistics will describe the following elements:

- Total Volume of Thrombosomes Infused (mL), computed as: ([patient body weight in kg] x [target dose in particles/kg, specific for dose cohort]) ÷ (Thrombosomes lot concentration in particles/mL)
- Interrupted Infusion (Yes/No)
- Reason for Interruption (Adverse Event, Infusion Site or Equipment not Functioning, Patient Declined Infusion, or Other)
- Total Number of Thrombosomes Particles Infused, computed as: (Thrombosomes lot concentration in particles/mL) x (Total Volume of Thrombosomes Infused in mL)
- Total Number of Particles Infused per Kilogram of Patient Body Weight (particles/kg), computed as: (Total Number of Thrombosomes Particles Infused) ÷ (patient body weight in kg)

A data listing will be provided to disclose the elements above for each patient. Note that standard units of calculation and presentation (i.e., particles vs. TGPU and particles/kg vs. TGPU/kg) will be selected prior to database lock. See also Section 3.1, **Table 1**, for more information.

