#### **6.5 Strata and Covariates**

No stratified analyses or covariate-adjusted analyses are planned for this study.

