## 7.2 Deviations from the Clinical Study Protocol

Deviations will be described in a single table by the numbers and percentages of patients in the Safety Population who were associated with at least 1 deviation and with at least 1 major deviation. Protocol deviations deemed “major” are defined as those that may significantly affect the completeness, accuracy, and/or reliability of the study data or that may significantly affect a patient's rights, safety, or well-being. The numbers and percentages of patients falling into each deviation category (listed below) will be summarized for major and minor deviations combined.

- Inclusion/exclusion criteria
- Informed consent issue
- Out of window visit
- Protocol required evaluation not completed
- Non-compliance with study drug administration
- Received excluded treatment
- Developed withdrawal criteria but not withdrawn
- Other

Patient-level data listings will be used to disclose the timing, category, and major/minor status of all deviations and, separately, just the deviations specifically associated with non-adherence to inclusion/exclusion criteria.

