### **14.3.8 Infused Thrombosomes**

Table 14.3.8.1      Summary of Thrombosomes Infusion Doses – Safety Population

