#### **16.2.7 Thrombosomes Infusion Data**

Listing 16.2.7.1 Thrombosomes Infusions – Safety Population

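### SAP 8.6 computes the infused dose from the target dose, so particles/kg equals the cohort target for every patient and a partial dose is never quantified

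*SAP*

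**What the plan says.** SAP 8.6 opens with its purpose: "A tabular summary of statistics describing the Thrombosomes infusion doses received by patients will be provided". It then lists the elements:

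- Volume: "Total Volume of Thrombosomes Infused (mL), computed as: ([patient body weight in kg] x [target dose in particles/kg, specific for dose cohort", divided by the lot concentration in particles/mL.
- Total particles: lot concentration times that volume.
- Particles per kg: "computed as: (Total Number of Thrombosomes Particles Infused) ÷ (patient body weight in kg".
- Delivery: "Interrupted Infusion (Yes/No", with a reason (adverse event, site or equipment failure, patient declined, other).

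The patient listing repeats the same elements. The outputs are Table 14.3.8.1 ("Summary of Thrombosomes Infusion Doses") and Listing 16.2.7.1 ("Thrombosomes Infusions"). The choice between particles and TGPU is left open until database lock.

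Three other places bear on the point. SAP 7.2 has a deviation category, "Non-compliance with study drug administration", reported as counts and percentages. SAP Table 1 uses the same volume formula, but its column is headed as an estimate. Protocol Table 6 directs that an infusion in progress be stopped if the patient withdraws, and SAP 5.2 keeps every infused patient in the Safety Population because enrolment is counted from the start of infusion.

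**The concern.** A dose-escalation study needs an exposure table that shows how much each patient got. The formula in SAP 8.6 is a planning formula: it gives the volume to prepare. Under the label of volume infused, it makes the table restate the plan.

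The cases that matter most are infusions stopped early, particularly for an adverse event. The plan foresees them, yet the dose columns would still show the full target for such a patient. A reader could not tell 10% of the dose from 90%, or see that the delivered dose was nearer a lower cohort's target. Because the targets double from cohort to cohort, a half dose is exactly the target of the cohort below. The flag also does not separate an infusion that was abandoned from one that was paused and then completed.

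**Working it through.** **Inputs.** Cohort targets T: 9.45 × 10^7, 1.89 × 10^8 and 3.78 × 10^8 particles/kg (SAP 2.1.1). Reference weight 70 kg and mean concentration 1.61 × 10^9 particles/mL (SAP Table 1). Infusion rate 1 ml/min (protocol 1.15.4). Eight patients per cohort (SAP 4). W is body weight and C is lot concentration. Neither document gives a rate of partial infusion or the fraction delivered, so the values used for these are assumptions.

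**1. The plan's own volumes.** V = W × T / C at 70 kg and 1.61 × 10^9:

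| Cohort | Computed (mL) | SAP Table 1 (mL) |
|---|---|---|
| 1 | 4.109 | 4.1 |
| 2 | 8.217 | 8.2 |
| 3 | 16.435 | 16.4 |

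They agree within 0.2%, so the formula in 8.6 is the one that produces the planned volumes.

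**2. Substitution through 8.6.**

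- Volume = W × T / C
- Particles = C × (W × T / C) = W × T
- Particles/kg = (W × T) / W = T

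Volume still varies with weight and lot, and total particles with weight, but only as planned amounts. Particles/kg is constant within a cohort. A check on 1,000 random pairs of weight (40–130 kg) and concentration (1.2–2.2 × 10^9) per cohort gave a ratio to target of 1.000 every time. The same cancellation occurs if TGPU is used throughout.

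**3. A single partial infusion.** With fraction f delivered, the patient received f × T; the SAP formula still returns T.

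| Cohort | Tabulated | f = 75% | f = 50% | f = 25% |
|---|---|---|---|---|
| 1 | 9.45 × 10^7 | 7.09 × 10^7 | 4.73 × 10^7 | 2.36 × 10^7 |
| 2 | 1.89 × 10^8 | 1.42 × 10^8 | 9.45 × 10^7 | 4.73 × 10^7 |
| 3 | 3.78 × 10^8 | 2.84 × 10^8 | 1.89 × 10^8 | 9.45 × 10^7 |

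**4. Cohort summary.** Assume seven patients at 100% of target and one at 100f%. Then mean = 100 − (100 − 100f)/8 and SD = (100 − 100f)/√8.

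| Delivered to one patient | True mean (% of target) | True SD | Tabulated mean, SD |
|---|---|---|---|
| 50% | 93.8 | 17.7 | 100, 0 |
| 75% | 96.9 | 8.8 | 100, 0 |
| 90% | 98.8 | 3.5 | 100, 0 |

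**5. Opportunity for a stop.** At 1 ml/min the 70 kg volumes take about 4, 8 and 16 minutes.

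**6. Protocol Table 2, a separate matter.** The footnote example is 70 × 9.45 × 10^7 / (1.7 × 10^9) = 3.89 ml, but 5.5 ml is printed. The column header uses 1.61 × 10^9 particles and 2800 TGPU per ml; the footnote uses 1.7 × 10^9 and 3400.

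**The case against.** The best case against the point is that it changes little. SAP 6.5 states "No stratified analyses or covariate-adjusted analyses are planned for this study", safety is summarised by assigned cohort, and the tables and listings that SAP Appendix 1 sends to the data monitoring committee include no infusion-dose output. Tests and escalation decisions, as specified, are therefore unaffected. All of this stands and limits the point to a reporting definition.

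Stops may be rare in infusions of 4 to 16 minutes, and no rate is given. If every infusion is completed, the formula is wrong only by ordinary preparation and delivery variation. That also stands: the one-in-eight scenario is an illustration, not a forecast.

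A flagged infusion may have been paused and completed, and then 100% of target is right. True, but the table cannot show which case applies, so this is a further reason to report the amount.

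The case report form may already record delivered volume. It is not among the documents. If it does, the written derivation still ignores it, and the fix becomes wording only.

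Departures are not hidden, since both the interruption flag and the deviation category exist. Agreed, but they give occurrence and reason, not amount.

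Finally, loss in the filter (0.7 ml priming volume, protocol 1.15.4) is not evidence either way: the documents do not say whether the 25 ml saline flush clears it. The conclusion does not use it.

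**Conclusion.** The point holds. As written, SAP 8.6 returns the cohort target for particles/kg in every patient, with an SD of 0, and neither document provides for analysing a delivered volume. That follows from the formulas alone and needs no assumption.

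The size depends on whether any infusion is incomplete. For an affected patient the tabulated dose is too high by the whole undelivered fraction; at cohort level, one half-dosed patient in eight overstates the mean by 6.2 percentage points of target and hides an SD of 17.7. The reach is Table 14.3.8.1 and Listing 16.2.7.1 only. It should be corrected because a stated rule gives a wrong reported dose precisely when the dose departs from plan, and the correction is cheap.

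The protocol Table 2 error is a text correction. Sites dose from a lot-specific table (protocol Appendix F.3) and SAP Table 1 carries a correct 4.1 mL example, so it is not evidence of misdosing.

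**What to change.** In SAP 8.6:

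- Relabel the present formula as planned volume (mL).
- Define total volume infused as the delivered volume recorded at infusion, that is, prepared minus residual.
- Derive particles/kg, TGPU/kg and percent of target from the delivered volume and the lot values, and show them in Table 14.3.8.1 and Listing 16.2.7.1. Giving both units also settles the choice left open until database lock.
- Where delivered volume was not recorded for a patient, show the planned volume labelled as such and leave the received dose missing. This may be needed: SAP 8.2 distinguishes protocol versions, which suggests that some patients were treated before this SAP.

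In protocol Table 2, correct the footnote example to 3.9 ml at 1.7 × 10^9 particles/ml (or 4.1 ml at 1.61 × 10^9), and use one set of concentrations in header and footnote.

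Cost: SAP wording, one protocol text correction, and at most one infusion-form field (none if delivered volume is already captured). Protocol Appendix F.3 does not describe measuring a syringe residual, so a new field would need a short site instruction. No extra patients.
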